All personnel will be properly trained in the protocol and procedures expected of them. In addition, refresher training may be conducted, as needed. Training logs will be kept in the study regulatory binders.

Monitoring of the Study

The sites will perform self monitoring of this study.

Source Data

All source documents will be maintained in the research chart for each subject. In addition, electronic medical records (EMR) may also be utilized by the study facility. It is the practice of the research facility to allow EMR access to monitors or auditors, if requested.

Study Timetable and End of Study

Patient recruitment is expected to be completed within 2 years of initiating the study. Once the final patient has been recruited, follow-up will last for 2 additional years. The study duration is estimated at 4 years.

During the time of enrollment, patients will be seen every three months. This includes the 3 month visit, 6 month visit, 9 month visit, and 12 month visit. At the 12 month visit, patients will be given the opportunity to continue in the study for an additional 12 months. This would include the 15 month visit, 18 month visit, 21 month visit, and 24 month visit.

Data Management

All data will be recorded on preprinted case report forms (CRF) suitable for electronic data capture. The case report forms will be kept in the patient's research chart. The research charts will be stored in a locked, secure location. Data will be entered by qualified personnel at the conclusion of study.

Statistical Methods

Sample Size

This trial will be a pilot study. Outcome estimates will form the basis for assessing the feasibility of designing a future large and definitive trial. One hundred fifty patients in each study arm will be enrolled (300 total patients). Since each patient will receive 2 vein grafts, on average, there will be approximately 300 vein grafts in each group (600 vein grafts total). This sample size will be large enough to detect whether a clinically important difference exists in terms of vein graft patency between the groups, but small enough that subject recruitment can be performed in an expedient manner, likely within the first 24 months of the study.

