This trial will not be designed or powered as a definitive clinical trial. Based on several previously published clinical trials, it is anticipated that 10-20% of vein grafts will be documented as occluded at the 1-year time point after CABG. Should ticagrelor improve graft patency and reduce vein occlusion from 20% to 10%, power calculations suggest that this pilot trial will have 96% power to detect a significant difference ($P<0.05$) between the groups. Alternatively, if ticagrelor were to decrease the occlusion rate from 15% to 10%, the power will be approximately 58%.

Statistical Analysis

All study data will be collected in a blinded fashion during the course of the trial. At 1- and 2-years after surgery, the CT coronary angiograms will be read and interpreted by board-certified radiologists with expertise in cardiac CT imaging. The radiologists will be blinded to study treatment assignment. The data analysis will also be performed in a blinded fashion, with un-blinding at the conclusion of the analysis. Study outcomes will be compared on an intention-to-treat basis according to the randomization study-group assignment. Vein graft occlusion, the primary outcome of the study, will be compared between the two randomization groups using a Fisher's exact test. To account for within-patient correlation and the possibility of multi-graft occlusion within individual patients, vein graft data will also be analyzed using logistic regression fit with generalized estimating equations methods. For secondary outcomes, continuous data will be compared between the two groups using two-sided Student's t tests, two-sample Wilcoxon rank-sum tests, or ANOVA, and a Fisher's exact test will be used for categorical data. Time to major adverse cardiovascular event will be determined for the study groups using the Kaplan-Meier method, and groups will be compared with a log-rank test. In accordance with intention-to-treat analysis, clinical and safety data will be analyzed for all randomized patients in the study. This will include data collected

from subjects who have dropped out of the trial or who refuse postoperative CT coronary angiography (5% expected refusal).

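### The named primary test, Fisher's exact test evidently applied to grafts, exceeds its 5% level if grafts in a patient are more than weakly correlated; the planned GEE model should be primary

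*Combined protocol and SAP*

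**What the plan says.** Patients are the randomised unit (Subject Enrollment and Randomization), and a patient needs at least one saphenous vein graft to be eligible (Inclusion Criteria). Under Sample Size, 150 patients per arm with two vein grafts on average become a count of grafts: "there will be approximately 300 vein grafts in each group (600 vein grafts total"). The event rate is also per graft: "it is anticipated that 10-20% of vein grafts will be documented as occluded" at 1 year. From these the plan states that "this pilot trial will have 96% power to detect a significant difference" for 20% versus 10%, and about 58% for 15% versus 10%.

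Under Statistical Analysis, vein graft occlusion, "the primary outcome of the study, will be compared between the two randomization groups using a Fisher's exact test". The next sentence begins "To account for within-patient correlation and the possibility of multi-graft occlusion within individual patients" and continues that "vein graft data will also be analyzed using logistic regression fit with generalized estimating equations methods". For secondary outcomes, "a Fisher's exact test will be used for categorical data".

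The documents do not name the unit of the Fisher test, define a patient-level occlusion endpoint, give an ICC, or say which of the two analyses decides the primary outcome.

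**The concern.** Fisher's exact test is valid when the units in the 2×2 table are independent. If those units are grafts and patients were randomised, grafts in one patient share that patient's biology and treatment. With positive correlation the table holds less information than its count suggests, so the P value is too small and a difference can be declared significant too often.

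The plan gives this correlation as its reason for running GEE, yet it attaches the primary outcome by name to the test that ignores it. With two unranked P values, the choice between them could also follow the result. The trial calls itself a pilot, but it says its size suffices to detect a clinically important difference and quotes power at P<0.05, so the P value will be read as a test. The same ambiguity affects stenosis: the GEE sentence may cover it as graft data, but the next sentence assigns Fisher to categorical secondary outcomes.

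**Working it through.** **Inputs from the documents.** 150 patients per arm; mean 2 vein grafts, minimum 1; about 300 grafts per arm; 10–20% of grafts occluded; significance at 0.05, sidedness not stated; 5% expected refusal of CT.

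**Assumptions.** ICC 0 to 0.4, equal in both arms. Grafts per patient: either all 2; or 1/2/3 with probabilities 0.25/0.50/0.25; or 1/2/3/4 with probabilities 0.30/0.45/0.20/0.05. The mean is 2 in each case. Occlusions follow a beta-binomial model.

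**Step 1: the plan's own power.** For two proportions with n independent units per arm, power = Φ[(|p1−p2| − z·√(2p̄(1−p̄)/n)) / √((p1(1−p1)+p2(1−p2))/n)].

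For 20% vs 10% and n = 300, the two standard errors are √(0.255/300) = 0.02916 and √(0.25/300) = 0.02887.
- Two-sided 0.05: (0.1 − 1.960×0.02916)/0.02887 = 1.48, power 93.1%.
- One-sided 0.05: (0.1 − 1.645×0.02916)/0.02887 = 1.80, power 96.4%.

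For 15% vs 10% the results are 45.7% two-sided and 58.2% one-sided. The stated 96% and 58% are therefore matched by independent grafts with a one-sided test. With n = 150 patients the results are 68.1% and 25.7% two-sided, or 78.5% and 36.8% one-sided, which match neither figure. This supports the graft as the intended unit.

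**Step 2: type I error of graft-level Fisher, two-sided 0.05, 15% occluded in both arms.** The two-graft row is an exact calculation (150 × 2 grafts per arm). The other rows are simulated, with 100,000 trials per setting.

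| Grafts per patient | ICC 0 | 0.1 | 0.2 | 0.3 | 0.4 |
|---|---|---|---|---|---|
| 2 each | 3.9% | 4.8% | 5.9% | 7.0% | 8.0% |
| 1–3 | 4.3% | 5.8% | 7.2% | 8.4% | 10.0% |
| 1–4 | 4.3% | 5.9% | 7.4% | 8.9% | 10.3% |

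At ICC 0.3 and 10% or 20% occluded, the error is 6.7% or 7.1% with two grafts each (exact), and 8.7–8.8% with 1–4 grafts. With two grafts each, the 5% level is passed at an ICC of about 0.14, 0.12 and 0.11 for 10%, 15% and 20% occluded. Below that, clustering only uses up Fisher's built-in conservatism.

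**Step 3: GEE in the same simulations.** Logistic model, independence working correlation. Per arm, the robust variance of the log odds is Σ(yᵢ − mᵢp̂)² / (n·p̂(1−p̂))², where patient i has yᵢ of mᵢ grafts occluded and n is the arm's graft total. Type I error is 4.85–5.25% over all 35 settings, and 4.6–5.3% in a separate, smaller set of runs reaching ICC 0.5. An identity-link GEE for the risk difference gives 4.9–5.4%. Fisher at patient level (any graft occluded) gives 3.5–3.8%.

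**Step 4: how often the choice matters.** With a true 15% vs 10% and ICC 0.3, the two tests disagree in 6% (two grafts) to 10% (1–4 grafts) of trials, almost always with Fisher significant and GEE not.

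**Step 5: power of the GEE test.** The design effect is 1 + (Σm²/Σm − 1)·ICC, which is 1 + ICC for two grafts and 1 + 1.35·ICC for 1–4 grafts. At ICC 0.3 the effective grafts per arm are 300/1.3 = 231 and 300/1.405 = 214. The Step 1 formula, two-sided, then gives 85.5% and 82.7% for 20% vs 10%. Simulation (8,000 trials per setting) agrees:

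| 20% vs 10% | ICC 0 | 0.1 | 0.2 | 0.3 | 0.4 |
|---|---|---|---|---|---|
| 2 each | 93% | 91% | 88% | 86% | 83% |
| 1–4 | 93% | 90% | 87% | 83% | 80% |

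For 15% vs 10%, GEE power is 45% at ICC 0 and 34–36% at ICC 0.3. These figures assume every patient is scanned. With 5% refusal (285 grafts per arm), the formula at ICC 0.3 uses 285/1.3 = 219 and 285/1.405 = 203 effective grafts and gives about 84% and 81% for 20% vs 10%.

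**The case against.** The strongest reply is that the valid analysis is already pre-specified. The sentence after Fisher plans GEE for exactly this reason, so the gap is one of ranking. That is accurate, and it makes the remedy cheap. It does not remove the problem, because Fisher is the only test tied by name to the primary outcome.

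Second, the unit of the Fisher test is an inference, and at patient level the test would hold its level. This stands as a caveat. But no patient-level endpoint is defined and 150 units per arm cannot give the stated power, so a patient-level reading would also need a change of text.

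Third, the size of the inflation depends on an unknown ICC and, for the larger figures, on an assumed spread of graft numbers. The simulation also ignores the stratification by site, diabetes and cardiopulmonary bypass, which could reduce the inflation somewhat; this was not quantified. All of this stands, and it is why the claim is conditional on more than weak correlation.

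Fourth, the trial is a declared pilot, which lowers the stakes. It does not remove them, given the power claim, and given that the estimates are meant to inform a larger trial, for which intervals that ignore clustering would be too narrow.

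**Conclusion.** The concern holds. If the Fisher test is run on grafts, as the plan's own counts indicate, it does not guarantee a 5% type I error. With two grafts each and ICC 0.3 the error is about 7%; with graft numbers varying from one to four it is about 9%. With nearly independent grafts the test is instead mildly conservative, at about 4%. These sizes rest on the assumed ICC range, the beta-binomial model and the assumed graft distributions. The argument for GEE does not depend on the true ICC, because GEE held its level in every setting examined. The inflation is moderate and the trial is a pilot, so this should be fixed but is not fatal to the design.

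**What to change.** - Name the patient-clustered logistic GEE (independence working correlation, robust standard errors, two-sided 0.05) as the single primary test of 1-year vein graft occlusion. State that it also applies to graft stenosis and to the 2-year graft analyses.
- Report the odds ratio and a risk difference (identity-link GEE or standardisation), each with a cluster-robust 95% confidence interval.
- Keep Fisher as a labelled sensitivity analysis, or apply it per patient (any vein graft occluded, yes or no). Name the unit either way.
- Restate power for the GEE test over a stated ICC range, giving the sidedness and allowing for the expected CT refusal. The one-sided basis of the stated 96% and 58% is a separate point, best corrected in the same edit.

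The cost is wording and a new power statement; the GEE is already planned and no extra data are needed. Most of the fall from 93% to 80–83% at ICC 0.4 comes from clustering, not from changing the test. For 20% vs 10%, the switch itself ranges from a gain of about 1 point at ICC 0 to a loss of about 6 points at ICC 0.3 with 1–4 grafts (Fisher 89.0%, GEE 82.7% in the separate runs). In that last case Fisher's higher power comes with its inflated type I error.

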Saphenous vein graft disease remains an unresolved medical problem. Many vein grafts occlude in the first year after bypass surgery, leading to adverse cardiovascular outcomes, including recurrent angina, myocardial infarction, and the need for repeat coronary intervention. While aspirin is the standard antiplatelet treatment after CABG surgery, 10-20% of vein grafts continue to occlude despite contemporary secondary preventative therapy. Compared to aspirin and other antiplatelet therapies like clopidogrel, ticagrelor treatment leads to a more pronounced platelet inhibition, and may substantially improve graft patency following CABG compared to aspirin. No data has yet to be collected regarding the impact of ticagrelor on saphenous vein graft patency following CABG. In this context, we seek to compare vein graft patency between patients randomized to receive aspirin therapy, the current standard of care, or ticagrelor treatment, starting in the early postoperative period, and continuing for 2 years after CABG.

Benefits, Risks and Ethical Assessment

It is anticipated that ticagrelor will improve vein graft patency in this clinical trial. To maximize the benefits and minimize the risks associated with ticagrelor, concomitant aspirin treatment will not be administered to patients randomized to receive ticagrelor in order to prevent bleeding complications associated with dual antiplatelet therapy. Patients who are randomized to aspirin treatment will receive 162 mg daily in keeping with current clinical guidelines, since a lower daily dose of 81 mg daily may be under-treatment and insufficient for antiplatelet therapy after CABG. In addition to graft patency at 1 and 2 years after surgery,

major adverse cardiovascular events and adverse bleeding events will be recorded in the 2-year interval after surgery. The study will be conducted with the highest ethical standards, in accordance with the applicable United States Food and Drug Administration (FDA) regulations and institutional review board requirements. This trial will be submitted to the FDA for review. Moreover, research ethics approval will be sought from the Western Institutional Review Board (WIRB).

Study Objectives

Primary Objective

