The primary objective of this clinical trial will be to evaluate whether, as compared to usual aspirin treatment, ticagrelor early after CABG prevents saphenous vein graft *occlusion* 1 year after surgery, as assessed by computed tomography (CT) coronary angiography, as well as 2 years after surgery via study extension.

Secondary Objective

The secondary objective of this clinical trial will be to evaluate whether, as compared to usual aspirin treatment, ticagrelor early after CABG prevents saphenous vein graft *stenosis*, defined as >50% narrowing of the graft, 1 year after surgery, as assessed by computed tomography (CT) coronary angiography, as well as 2 years after surgery via study extension.

Exploratory Objectives

Additional exploratory objectives of this clinical trial will include the impact of ticagrelor treatment, as compared to aspirin, on the incidence of major adverse cardiovascular events (mortality, myocardial infarction, cerebrovascular accident, hospitalization for coronary ischemia, and need for coronary intervention) and bleeding events in the first year and second year study after CABG (Appendix B). It is recognized that the study will be under-powered in the evaluation of these outcomes, which will be defined using the previously published definitions from the CURE and CASCADE trials [30, 39, 44]. Specifically, major bleeding episodes will be defined as substantially disabling bleeding, intraocular bleeding leading to the loss of vision, or bleeding necessitating the transfusion of at least 2 units of blood. Major bleeding is classified as life-threatening if the bleeding episode is fatal, leads to a reduction in the hemoglobin level of at least 5 grams per deciliter or to substantial hypotension requiring the use of intravenous inotropic agents, if it necessitates a surgical intervention, if it is a symptomatic intracranial hemorrhage, or if it necessitates the transfusion of four or more units of blood. Minor bleeding episodes will include other hemorrhages (i.e. nose bleeds) that lead to the interruption of the study medication.

Study Plan and Procedures

Overall Study Design

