Compounding Docs will prepare identical capsules containing either 81 mg of aspirin or 90 mg of ticagrelor. These prepared capsules will appear identical for the purpose of blinding in this study. Patients in the trial will be assigned to receive either one aspirin 81 mg capsule 2 times per day (Arm A – aspirin) or one ticagrelor 90 mg capsule 2 times per day (Arm B – ticagrelor). Compounding Docs will prepare pill bottles containing 180 capsules to cover for a 3-month supply. The blinded capsules will be stored at room temperature (25°C), as indicated on the bottle container label. These pill bottles will then be submitted to the Boca Raton Regional Hospital (BRRH) pharmacy. Ordering and dispensing of the blinded study medication will be coordinated by the BRRH pharmacy. Shipment of study medication to the second recruitment site at the University of Ottawa Heart Institute (Ottawa, Ontario, Canada) will also be coordinated by the BRRH pharmacy. After surgery, each trial participant will be provided with a 3-month supply of study medication, and a new pill bottle will be provided to each patient every 3 months over the course of the 1- or 2-year trial enrollment.

The study population will include all patients undergoing CABG over the study period at the Lynn Heart and Vascular Institute of the Boca Raton Regional

Hospital in Boca Raton, Florida, and the University of Ottawa Heart Institute in Ottawa, Ontario, Canada. Patients undergoing on-pump or off-pump CABG will be eligible for this study, as long as at least one saphenous vein graft is used. Patients undergoing concurrent valve repair or replacement surgery will also be eligible, unless postoperative warfarin anticoagulation is anticipated (i.e. mechanical prosthetic valve). CABG patients will be pre-screened and evaluated for study eligibility in the perioperative period (Appendix A). Study eligible patients will be selected and approached by the study coordinator to explain the trial. Consent and randomization will occur within 5 days after surgery. Randomization will be stratified based on the surgical site, the presence of diabetes mellitus, and the use of cardiopulmonary bypass (on-pump or off-pump).

[figure not shown]

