Unlikely related – no temporal association, or the cause of the event has been identified, or the drug, biological or device cannot be implicated

Possibly related – temporal association, but other etiologies are likely to be the cause; however involvement of the drug, biological, or device cannot be excluded

Probably related – temporal association and other etiologies are possible but unlikely

Recording of Adverse Events

Adverse events will be recorded for study subjects while they are enrolled in the trial (maximum 2 year enrollment). Serious adverse events that occur at any time after the inclusion of the subject in the study (defined as the time when the subject is randomized) up to 30 days after the subject completed or discontinued the study medication must be reported. The subject is considered to have completed the study either after the completion of the last visit or contact (e.g. phone contact with the investigator or designee), or 30 days after the last dose of the study medication, whichever is later.

As noted above, the incidence of major adverse cardiovascular events (mortality, myocardial infarction, cerebrovascular accident, hospitalization for coronary ischemia, and need for coronary intervention) and bleeding events will be recorded (and noted as adverse events) for trial subjects in the 2 year period after CABG. If, during trial enrollment, a participant develops a major adverse cardiovascular event or major bleeding event, the TARGET blinded study

medication will be discontinued. The participant will then receive open label treatment as indicated by the clinicians involved in the patient's care.

The following variables will be collected for each AE:

- Adverse event description
- The date when the AE started and stopped
- Whether the AE is serious or not
- Investigator causality rating against the study medication
- Action taken with regard to study medication
- Whether AE caused subject's withdrawal from study
- Patient outcome

In addition, the following variables will be collected for SAEs:

- Date AE met criteria for serious AE
- Date investigator became aware of serious AE
- Reason AE is serious (i.e. hospitalization, probable cause of death)
- Dates of hospitalization, discharge, and/or death
- Whether autopsy performed
- Investigator causality rating against the study medication or other medications

Reporting of Serious Adverse Events

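### Bleeding has no analysis that allows for censoring although the second year is optional; the plan's default Fisher test at 2 years would treat unobserved time as bleed-free

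*Combined protocol and SAP*

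**What the plan says.** **Objective.** Bleeding and MACE share one exploratory objective (Study Objectives, Exploratory Objectives): "Additional exploratory objectives of this clinical trial will include the impact of ticagrelor treatment", compared with aspirin, on MACE and on "bleeding events in the first year and second year study after CABG (Appendix B"). The same paragraph concedes limited power: "It is recognized that the study will be under-powered in the evaluation of these outcomes".

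**Method.** Under Statistical Methods, Statistical Analysis, a sentence on secondary outcomes lists tests for continuous data and ends "and a Fisher's exact test will be used for categorical data". The next sentence reads "Time to major adverse cardiovascular event will be determined for the study groups using the Kaplan-Meier method", with a log-rank comparison. No method is named for bleeding. Clinical and safety data are analysed for all randomised patients, including data collected from dropouts. One analysis follows when the last patient has passed 1 year, and a second when all have passed 2 years.

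**Length of follow-up.** Overall Study Design has each patient take part for 1 year and then be invited to a second; the study drug is resupplied "over the course of the 1- or 2-year trial enrollment". Study Timetable and End of Study places the offer at the 12-month visit. Expected uptake is not stated.

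**Recording of events.** Recording of Adverse Events says "Adverse events will be recorded for study subjects while they are enrolled in the trial (maximum 2 year enrollment"). The same section also speaks of recording MACE and bleeding in trial subjects over the 2 years after surgery. Benefits, Risks and Ethical Assessment likewise says "major adverse cardiovascular events and adverse bleeding events will be recorded in the 2-year interval after surgery". Neither 2-year statement makes an exception for patients who decline the extension.

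**The concern.** Fisher's test on all randomised patients needs a yes or no for each one. A patient who leaves at month 12 without a bleed has no observed second year. If that patient stays in the 2-year denominator, the only available entry is no bleed. The 2-year proportion then mixes bleeding risk with willingness to continue.

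MACE, which has the same follow-up and sits in the same objective, is given a method that censors such patients. Exploratory status therefore does not explain why bleeding is not.

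Bleeding is the risk the protocol cites when it withholds aspirin from the ticagrelor arm, and the Sample Size section says the pilot's estimates will inform a definitive trial. A distorted 2-year bleeding estimate would be carried into that design.

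**Working it through.** The plan gives no figure for bleeding (rate, power or uptake), so there is none to reproduce. All rates and uptakes below are assumptions. Only 150 patients per arm comes from the protocol.

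**Formulas.** Let r be the annual risk of a first bleed and u the share of patients who accept year 2.
- True 2-year risk = r + (1 − r)·r
- Crude 2-year proportion, everyone in the denominator = r + (1 − r)·u·r

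**Main illustration: r = 12% aspirin, 18% ticagrelor.**
- True, aspirin: 0.12 + 0.88 × 0.12 = 22.6%. True, ticagrelor: 0.18 + 0.82 × 0.18 = 32.8%. Difference 10.2 points, risk ratio (RR) 1.45.
- Example, 85% aspirin and 65% ticagrelor uptake: 0.12 + 0.88 × 0.85 × 0.12 = 21.0%; 0.18 + 0.82 × 0.65 × 0.18 = 27.6%. The difference is 6.6 points, so 1 − 6.62/10.20 = 35% is lost.

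| Uptake, aspirin / ticagrelor | Crude aspirin | Crude ticagrelor | Difference (points) | RR | Change in difference |
|---|---|---|---|---|---|
| 80% / 80% | 20.4% | 29.8% | 9.4 | 1.46 | −8% |
| 85% / 75% | 21.0% | 29.1% | 8.1 | 1.39 | −21% |
| 85% / 65% | 21.0% | 27.6% | 6.6 | 1.32 | −35% |
| 65% / 85% | 18.9% | 30.5% | 11.7 | 1.62 | +15% |

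Equal uptake leaves the ratio essentially intact and shrinks the difference. Unequal uptake moves both, in a direction set by which arm declines more. With no true difference (12% in both arms), 85%/65% uptake gives 18.9/21.0, a spurious RR of 0.90 for ticagrelor; 65%/85% gives 1.11.

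**Sensitivity of the 35% figure.** Two assumptions push it upwards.
- *Constant risk.* The label in Appendix C (text introducing Table 1) puts about half of bleeding events in the first 30 days. If year-2 risk is halved (6% and 9%), the true risks are 17.3% and 25.4% (8.1 points) and the crude ones 16.5% and 22.8% (6.3 points): 22% lost.
- *Patients who decline keep the on-ticagrelor risk.* They receive no more capsules. If their year-2 risk falls to the aspirin rate, true ticagrelor risk is 0.18 + 0.82 × (0.65 × 0.18 + 0.35 × 0.12) = 31.0%, a difference of 8.5 points: 22% lost. Under this assumption the loss at 80%/80% disappears.
- Both changes together: true difference 7.2 points, crude 6.3: 13% lost.

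**Power, 150 per arm, assumed annual risks 5% and 10%.** Simulation with 1,500 runs, constant hazard and two-sided 0.05 tests:

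| Uptake, aspirin / ticagrelor | Fisher, all randomised | Log-rank, censored |
|---|---|---|
| 100% / 100% | 55% | 61% |
| 80% / 80% | 53% | 59% |
| 50% / 50% | 44% | 52% |
| 80% / 50% | 27% | 55% |

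The gap of about 6 points in the first row exists with complete follow-up, so it is not caused by the extension. The gap of 28 points (55 − 27) in the last row is mostly due to unequal uptake. With no true difference and 80%/50% uptake, rejection was 5.7% for Fisher and 4.9% for log-rank.

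At 1 year extension uptake plays no part: exact Fisher power at 5% versus 10% is 30% whatever the later uptake.

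**The case against.** A reader might infer that the plan orders Fisher's test for bleeding and counts patients who leave as bleed-free. It says neither. The Fisher clause stands in a sentence about secondary outcomes, and bleeding is exploratory. Including the data collected from dropouts is not the same as imputing non-events. The wording on first-year and second-year events would permit a year-2 analysis restricted to extension participants. This stands: both readings are inferences from the default rule. If that rule does not apply, however, bleeding has no specified analysis, and the same sentence is needed.

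A reader might also infer that a ticagrelor excess will be hidden. The documents do not support a direction. The label's discontinuation for adverse reactions (7.4% versus 5.4%) compares ticagrelor with clopidogrel, and it concerns stopping drug, not leaving follow-up. The protocol keeps patients in follow-up after a serious bleed or an anticoagulation interruption. A 2-point gap in drug stopping does not establish uptake gaps of 10 or 20 points, and the opposite imbalance would exaggerate the relative excess.

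Finally, the protocol calls itself a pilot and admits low power for these outcomes, and the inflation of false positives in the simulated case was small. That lowers the stakes. It does not justify a crude proportion when the plan already holds a better method.

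**Conclusion.** The gap is real and confined to the 2-year comparison. Follow-up is 1 or 2 years by the patient's choice, recording is tied to enrolment, all randomised patients are analysed, and the only method that handles unequal follow-up is reserved for MACE. A crude 2-year proportion would understate bleeding risk in both arms. With equal uptake the risk difference shrinks modestly (about 8% at 80% uptake under the main assumptions) and the ratio holds. With unequal uptake the comparison is biased in a direction that cannot be known beforehand: from 13% to 35% of the difference lost at 85% aspirin and 65% ticagrelor uptake, depending on the year-2 assumptions, and about 15% gained under the reverse pair with constant risk. None of these is a prediction, since the documents give no uptake and no bleeding rates for this comparison. The change is worth making because it costs almost nothing.

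**What to change.** In Statistical Analysis:
- Analyse time to first major bleed and time to first bleed of any grade alongside MACE: cumulative incidence by arm at 12 and 24 months, log-rank test, and hazard ratio with 95% confidence interval. Censor at last contact and treat death as a competing event.
- Keep the 1-year comparison, and report extension uptake by arm.

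In Recording of Adverse Events and in Benefits, Risks and Ethical Assessment: reconcile recording during enrolment with the 2-year recording stated in both sections, and say which applies to patients who decline the extension. If they agree to continued 3-monthly telephone calls, use those calls for major bleeding and MACE only. Minor bleeding is defined through interruption of study medication, so a patient without capsules cannot meet the definition; state how the any-grade analysis treats such patients, for example by censoring at the end of enrolment.

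Cost: a few sentences, slightly more analysis work and a small number of calls. Adverse event start dates are already collected. One limitation remains: the log-rank test assumes that declining the extension is unrelated to bleeding risk, so uptake by arm should be read with the result.
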